“Major” orthopedic procedures are defined, for the purposes of this study, as operations that are equal to or greater than 90 minutes in “skin-to-skin” time (initial incision to skin closure). Orthopedic procedures (hip reconstruction and spine stabilization) are the most common major procedures that

children with SNI are exposed to, although they also experience many “minor” procedures, such as gastrostomy tube placement, tendon releases, and dental procedures. We are focusing on the longer procedures for this pilot study both because anecdotally, parents have not described the same degree of concern with shorter operations, and for methodological reasons, to improve the opportunity to identify this phenomenon.

Study participant eligibility criteria

Inclusion Criteria

- 1) Children with SNI, including the Gross Motor Function Classification System (GMFCS) levels II to V and Communication Function Classification System (CFCS) levels II to V, and;
- 2) undergoing major orthopaedic surgical management of musculoskeletal pathology (spine or hip; major defined as a greater than or equal to 90 minute procedure with skin-to-skin contact) at the BC Children's Hospital and;
- 3) between 5 and 18 years at the time of their surgical procedure

Exclusion Criteria

- 1) GMFCS level I and CFCS level I
- 2) Non-English-speaking Parents/Caregivers

Control group - justifications and eligibility criteria

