We aim to recruit 5 control participants specifically for our biomarker analysis (ie. we will only collect demographics and blood samples). The inclusion of this control group allows for a direct comparison of the pre-, peri-, and post-operative inflammatory responses between children with SNI vs neurotypical patients undergoing similar procedures. This is essential for discerning whether any observed altered biomarkers levels specific to children with SNI (ie. and not seen in neurotypical patients), or if they reflect a generalized postoperative inflammatory response. This comparison strengthens the interpretation of our biomarker findings by providing a baseline, which will reduce the risk of misattributing inflammation-related findings solely to the presence of SNI rather than the general surgical response. Additionally, the inclusion of controls improves the clinical relevance of our study, as it will help determine whether children with SNI exhibit exaggerated, prolonged, or distinct inflammatory responses compared to their neurotypical counterparts. These insights will be critical for guiding future research and potential interventions aimed at mitigating PoFD in children with SNI.

Inclusion Criteria

- 1) Neurotypically developing children (GMFCS I and CFCS I)
- 2) Undergoing major orthopaedic surgical management of musculoskeletal pathology (spine or hip; major defined as a greater than or equal to 90 minute procedure with skin-to-skin contact) at the BC Children's Hospital
- 3) Between 5 and 18 years of age at the time of their surgical procedure

Exclusion Criteria

- 1) Non-English-speaking parents/caregivers

Participant Screening and Recruitment

Participants for this study will be recruited in-person through the BC Children's Hospital Orthopaedic Clinics, including the Orthopedic Cerebral Palsy Clinic (CP Clinic) and the Spine Clinic. Study participants

will receive \$100 remuneration for their participation in the study, and control participants will receive \$50 remuneration for their participation.

Participant Screening

1) Screening through standard-of-care clinical visits

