The BCCH Orthopedic Clinic (Hip and Spine) will serve as the main recruitment site, where children with SNI and neurotypical children with scoliosis attend regular orthopedic visits. Prospective participants will be identified from a list of patients who will be attending a regular clinic visit at both the Orthopedic Cerebral Palsy Clinic and Spine Program by respective clinic Research Assistants (RAs). Following identification, the RAs at each respective clinic will screen patients as standard for their own studies and flag patients that align with our study's inclusion criteria; for the Hip Clinic, this will be for the Hippy Lab's Outcomes of Hip Interventions for Children with Cerebral Palsy – An International Multi-Centre Prospective Comparative Cohort Study (Ethics ID # H14-01402) study using PowerChart prior to patients' clinical visits, and Spine Program RAs will screen patients independently. The Clinic RAs will then provide the [name] Lab RA with a list of their potential participants with information relevant to the Post-Op Changes Study. Using this list, the [name] Lab RA will then screen for Post-Op Changes Study inclusion criteria (age, GMFCS and CFCS status, on track for major hip/spine surgery), and will coordinate with Clinic RAs to visit these participants at their upcoming pre-operative appointment.

2) Screening through surgical slate – Hip Clinic

The [name] Lab RA will receive an operating room slate for the patients scheduled for surgery in the upcoming month from the Hip and Spine Clinics' Medical Office Assistant(s), along with the dates of surgery and pre-operative appointments. These participants may then be screened for our inclusion criteria by the [name] Lab Research Nurse using PowerChart; for eligible participants, arrangements will then be made for participants to be approached and recruited at their pre-operative appointment.

3) Screening through CST Cerner

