The Medical Student Research Assistant with Level 2 Cerner access will filter their search on CST Cerner specifically for the 3 surgeons whose patients we have obtained permission to recruit from: Drs. [name], [name], and [name]. This will result in a list of the operating schedule and pre-operative appointments for each surgeon. The RA will then access the patients' charts for those who have a confirmed surgery date or pre-operative visit to screen for our inclusion criteria to determine if they are eligible to be a study participant or a control. Screened eligible patients will be confirmed with the Orthopaedic team RAs prior to approaching the patient. With this, we will track all patients who would be eligible, as well as patients that we approached, in a password protected Excel Spreadsheet housed under our lab's V Drive. We have attached the spreadsheet under Recruitment documents which includes all data we will be collecting as part of this screening.

Participant Recruitment

1) Recruitment at regular clinic visit:

During the standard-of-care clinical visit of patients who will likely undergo surgery within ~6 months (as identified by the RAs/team of each clinic conducting screening), the patient's clinician will ask the

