We aim to recruit 12 study participants and 5 control participants for this pilot study, which will be useful to 1) test the feasibility and acceptability of our methods and tools for later use on a larger scale, and 2) allow us to describe patterns in preliminary data to identify early associations that may guide the methodology of a larger study. A sample size of 12 study participants and 5 control participants is likely feasible, as the Orthopedic Clinic sees an average of 50 children for hip/spine surgery each year.

STUDY PROCEDURES

The study will include a total of six timed assessments (**Figure 1**). This includes three primary study assessments to collect functional survey and biomarker data: 1) at baseline (within three months of surgery), 2) 6 weeks post-operatively, and 3) 6 months post-operatively. Additionally, we will conduct three biomarker-specific collections during the time of surgery immediately prior to the initiation of the procedure, 12-24 hours post-operatively, and 1-2 weeks post-operatively, based on the physiology of the sequence of the innate and adaptive immune response systems. Most study assessments will be timed at standard of care visits at the BC Children's Hospital. Each primary study visit will take approximately 25-30 minutes. Total time of participation will be 1.5 – 2 hours. Measures will be taken congruently with standard clinical care data collection where possible to reduce participation burden. Some participants may be recruited exclusively for functional/quality of life data collection while the team awaits approvals for blood collection and storage, to allow for an increased sample size.

Baseline Data Collection

Study participants who have consented will undergo a total of 3 primary study visits and 6 biomarker collections (**Figure 1**). At Study assessment #1, demographic information for the child (including variables such as age, sex, race/ethnicity, primary diagnosis, GMFCS/CFCS/MACS score) and demographic information of the parent/caregiver (age, sex, relationship to child, employment status, household income, race/ethnicity, distance from home to primary medical facility) will be collected. Outcome measures (see below) will also be collected. Baseline data collection aims to capture the initial status of participants before any surgical intervention, providing a reference point for post-operative comparisons.

Outcome Measures

The follow study procedures correspond to our primary aims:

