
With respect to statistical analysis of our control group, our primary analysis will involve a group comparison at each timepoint to assess whether, and to what extent, any biomarkers are altered (increased or decreased) in children with SNI compared to our controls. Given the large biomarker panel (approximately 120 biomarkers), data visualization using volcano plots will be employed. Multiple comparison adjustments will be applied using the false discovery rate (FDR) correction method (Benjamini-Hochberg). Biomarker significance will be determined based on effect size thresholds, specifically log2(fold change), with a significance level set at 5% (Type I error). Additionally, associations between biomarkers and study variables (e.g., age, sex) will be explored using Wilcoxon rank-sum tests.

Outcomes

The following outcomes will be utilized to deem our study feasible and acceptable:

Feasibility:

1. Consent rate: An average consent rate of 2-3 children/month
2. Protocol delivery: The protocol can be implemented with >85% protocol delivery.
3. Outcome completion: >85% of outcomes will be complete and measured as scheduled.

Acceptability:

4. General positive report on participation based on semi-structured interview

Secondary outcomes; we will explore pre- and post-operative data to describe patterns in:

1. Function of the child, as scored on the CPCHILD;
2. Quality of life of caregiver, as described by supplemental question;
3. Inflammatory profile of child

DATA STORAGE

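### The SNI v control biomarker contrast is open to confounding by operation, because nothing ties the controls' hip:spine mix to that of the SNI children

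*Protocol*

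**What the plan says.** The Protocol's section on the control group presents the controls as the means of telling an SNI-specific inflammatory response from the response to surgery in general, through a comparison "between children with SNI vs neurotypical patients undergoing similar procedures".

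The operation criterion is the same in both groups. SNI children are those "undergoing major orthopaedic surgical management of musculoskeletal pathology (spine or hip; major defined as a greater than or equal to 90 minute procedure", and the control criterion reads "Undergoing major orthopaedic surgical management of musculoskeletal pathology (spine or hip; major defined as a greater than or equal to 90 minute procedure".

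Under Participant Screening, route 1 describes the main recruitment site as the clinic "where children with SNI and neurotypical children with scoliosis attend regular orthopedic visits". Hip Clinic screening on that route is done for a study titled "Outcomes of Hip Interventions for Children with Cerebral Palsy". Route 2 uses the operating slate from the Hip and Spine Clinics. Route 3 searches the lists of three surgeons "to screen for our inclusion criteria to determine if they are eligible to be a study participant or a control".

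Sample Size Justification sets the numbers: "We aim to recruit 12 study participants and 5 control participants for this pilot study". Under Data Analysis (Blood collection), the SNI v control comparison is given as: "our primary analysis will involve a group comparison at each timepoint". Age and sex are the only study variables named there, as examples. The only stratification named in Data Analysis is by GMFCS 5 sub-category.

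**The concern.** The controls are there to stop a general surgical response being read as a feature of SNI. They can do this fully only if the two groups have a comparable mix of operations. The SNI group may combine hip reconstruction and spine surgery, while the recruitment text points mainly to scoliosis patients for controls. If the control group turns out mostly or wholly spine, the pooled contrast mixes two differences: SNI v neurotypical, and hip v spine.

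The Protocol gives some reason not to take hip and spine as interchangeable. At 1-2 weeks it has spine patients sampled by bedside nurses on the ward and hip patients sampled at a non-routine laboratory collection, which suggests different post-operative courses. That does not show a biomarker difference, but it means similarity should not be assumed.

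Controls give blood before incision, at 12-24 hours and at 6 months. A difference in response to the operation can affect only the two post-operative draws. At stake is which markers are carried forward as SNI-related into the planned larger study.

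**Working it through.** The Protocol states no figure for this point, so there is none to reproduce. The 12 + 5 sample rests on availability (17 of about 50 operations a year, 17/50 = 34%), not on a power calculation.

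**Reading the recruitment text**

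- Route 1: the only neurotypical group named has scoliosis, and the Hip Clinic flow is a cerebral palsy cohort, which would not be expected to yield neurotypical hip controls.
- Routes 2 and 3: neither is limited to scoliosis, so hip controls are possible.
- No route sets a number or share of controls by operation.

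**Size of the bias**

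Let h_S and h_C be the hip shares in SNI children and controls, and D the hip-spine difference in a marker after surgery. With no true SNI effect, the pooled contrast has expectation

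bias = (h_S − h_C) × D.

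The documents give none of these three inputs. The table assumes all five controls are spine (h_C = 0). The rejection rates come from a simulation of a two-sample t-test, 12 v 5, normal data with SD 1, nominal 5% per marker and 40,000 runs. The t-test is also an assumption, because the Protocol names no test for this contrast.

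| D (SD) | h_S = 25% | h_S = 50% | h_S = 75% |
|---|---|---|---|
| 0.5 | bias 0.125, rejects 5.4% | 0.25, 6.7% | 0.375, 9.5% |
| 1.0 | 0.25, 5.5% | 0.50, 10.5% | 0.75, 21.6% |
| 1.5 | 0.375, 5.8% | 0.75, 15.3% | 1.125, 38.9% |

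The direction depends on the sign of D, which is unknown. If h_C = h_S, the bias is 0 for any D.

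**Could balance be left to chance?**

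Suppose the SNI group is 6 hip and 6 spine, and each control is equally likely to be either. The hip shares differ by at least 0.30 when 0, 1, 4 or 5 of the controls are hip: (1 + 5 + 5 + 1)/2^5 = 12/32 = 37.5%. Even if hip controls were as easy to find as spine controls, a marked imbalance would be common with five.

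**What a within-spine contrast can show**

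If a rank test were used, the smallest two-sided exact p is 2/C(n1 + n2, n1). The first Benjamini-Hochberg threshold over about 120 markers is 0.05/120 = 0.00042.

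- Pooled, 12 v 5: 2/6188 = 0.00032, so a single marker can pass.
- Spine only, 6 v 5 (half the SNI group spine, all controls spine): 2/462 = 0.0043. Because 0.0043/0.00042 is a little over 10, at least 11 markers would have to reach that minimum together.

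**The case against.** The best defence is that the eligibility text, not the description of who attends a clinic, governs who can be a control. That text allows hip or spine surgery in the same words for both groups. A reader might infer from the recruitment section that controls are drawn only from scoliosis patients. The documents do not support that: the sentence describes attendance, and the slate and surgeon-list routes carry no such limit. This part of the defence stands, so confounding is an uncontrolled risk and not a settled feature of the design.

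A reader might also infer that the analysis is fixed as unadjusted. The Protocol names no model or test for the group comparison, its list of study variables is open, and surgery-specific data are to be extracted for context. Covariates may be left to an analysis plan that is not shown. This stands in part. However, enrolment of controls is fixed by the Protocol, and if all five were spine, no later analysis could compare SNI hip children with neurotypical hip children. False discovery rate control limits chance findings; it does not remove confounding.

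Finally, the Protocol says the controls reduce the risk of misattribution, not that they remove it. Spine controls do serve that aim for SNI spine children.

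**Conclusion.** The claim of similar procedures rests on a shared eligibility criterion alone. The recruitment routes point mainly to spine controls, and nothing in the Protocol balances, stratifies or separates by operation. The pooled SNI v control contrast is therefore open to confounding by operation.

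The documents do not fix the size. The tabulated values of 0.125 to 1.125 SD follow wholly from assumed hip shares, assumed hip-spine differences and all-spine controls, and should not be read as estimates of bias in this study. In the milder scenarios the effect on the error rate is slight (5.4% to 5.8% at a 25% hip share). It becomes serious only when both the share and the difference are large.

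This is a minor point. The primary outcomes are feasibility and acceptability, and no primary conclusion depends on this contrast. It is worth settling before controls are enrolled, because the operation mix cannot be changed afterwards.

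**What to change.** **Control group and screening sections.** State that the five controls are enrolled to follow the SNI hip:spine mix as far as hip controls are available, and that operation type is recorded for controls. The control section now limits their data to demographics and blood. With a 6:6 SNI group, two hip and three spine controls would leave a share difference of 0.50 − 0.40 = 0.10, against 0.50 with all-spine controls.

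**Data Analysis (Blood collection).** Report the contrast within spine cases, and within hip cases if there are any hip controls, beside the pooled contrast. State that pooled differences will not be attributed to SNI if the operation mix differs between groups.

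**Optional additions.** Change from the pre-incision sample can be added to deal with differences present before surgery. It does not address this confounding, because a hip-spine difference in surgical response lies in the change itself. If drug exposure is to be tabulated by group, the Protocol must say that record extraction also covers controls.

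**Cost.** No added patients, slightly slower control recruitment and a small amount of extra data on controls. The within-operation contrasts will be imprecise: 6 v 5 if all controls are spine, or 6 v 3 (smallest exact rank p 2/84 = 0.024) if the mix is followed as above. They should be presented as descriptive. Replacing the pooled contrast with the spine-only one is a debatable trade, so both should be shown.

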In this pilot study, we will evaluate the feasibility and acceptability of our protocol to explore the functional post-operative trajectory in a developmentally and neurologically impaired pediatric population. We will evaluate consent rate, protocol delivery and outcome completion, and acceptability. We will also describe common elements of the experience of these children and their families, including information from a functional skills questionnaire, parental descriptions of pre-post abilities, and parental descriptions of their own quality of life. The objectives of our research are:

Primary outcomes

Objective 1: To evaluate the feasibility and acceptability of our study protocol for children and families living with SNI.

To evaluate feasibility we will use the following evaluation points:

1. Consent rate: The overall average consent rate of children/month.
2. Protocol delivery: The percent of on/off protocol children.
3. Outcome completion: The percent of children with complete outcome measures.

To evaluate acceptability, we will conduct end-of-study interviews with caregivers to assess outcomes related to the ease and utility of participating in the study, including our methods of data collection.

Secondary outcomes:

Our secondary aim is to explore patterns of recovery in children with SNI during the peri-operative period. We will assess:

Objective 1: Function in children with SNI, including exploring patterns in specific domains of gain/loss.

Objective 2: Quality of life in children with SNI and their families

Objective 3: Profile of inflammatory biomarkers to compare children's inflammation levels peri-operatively.

HYPOTHESIS

We expect to confirm feasibility and acceptability of conducting peri-operative research in this population, with at least 12 children consented in 1 year and >85% protocol delivery and outcome completion. We anticipate to be able to measure PoFD, quality of life for children and caregivers, and inflammatory biomarkers.

METHODOLOGY

Study Design

This study will use an observational, pre-post intervention design to evaluate our methods of documenting the post-operative functional trajectory and quality of life in children with SNI and their families during the peri-operative period. We will explore the functional abilities and quality of life of children with SNI and their parent/caregivers pre- and post- major orthopaedic surgery, and we will undertake measurements of inflammatory biomarkers

Study Population

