To assess feasibility, we will evaluate three primary feasibility outcomes at the time of data analysis. We will calculate consent rate, which is the overall average consent rate of children/month; protocol delivery, which is the percent of on/off protocol children; and outcome completion, the percent of children with complete outcome measures.

To assess acceptability, anytime after the 6-week timepoint, we will conduct semi-structured interviews with families to assess their experience in participating in this study. We will also ask families if there were any domains that were not included in our standardized functional/quality of life questionnaire and questions. Parents may select from pre-identified domains as prompts (including pain, energy, and sleep), and may also provide additional insight through open-ended conversation. Interviews will be recorded, transcribed, and analyzed using thematic analysis.

The follow study procedures correspond to our secondary aims:

Our primary tool for this study to measure our outcomes of function and quality of life will be the Caregivers Priorities and Child Health Index of Life with Disabilities (CPCHILD) Questionnaire³⁵, which has

been proved to be both valid and reliable^{35,36}. The CPCHILD Questionnaire is used to assess the effectiveness of interventions aimed at improving and preserving outcomes for children aged 5-18 years old with severe disabilities, based on caregivers' perspectives. This questionnaire includes 37 items collected from the parent/caregiver measured across six domains: Personal Care/Activities of Daily Living; Positioning, Transferring, and Mobility; Comfort and Emotions; Communication and Social Interaction; Health; Child's Overall Quality of Life; with additional sections for Importance of Items to Child's Quality of Life, Facts about the Child, and Facts about the Caregiver. From responses, standardized scores can be retrieved on a scale of 0 to 100 for each domain, as well as a total score, and we will be examining comparisons at the item-level pre/post-operatively.

Parents/caregivers will also be asked to answer two supplemental questions to provide further insight into 1) other areas of function that were not described by CPCHILD and 2) the quality of life of caregivers.

Blood collection of study participants

To collect information regarding the peri-operative inflammatory profile, we will collect blood samples from study participants at all study time points:

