- **Timepoint #1** (pre-operative appointment): during routine care through venipuncture by C&W Lab Technicians. An additional finger prick will be taken by technicians (non-routine).
- **Timepoint #2** (surgery): prior to incision through peripheral venous line by OR staff
- **Timepoint #3** (12-24 hours post-op): by bedside nurses in T6 or PICU
- **Timepoint #4** (1-2 weeks post-op)
 - Hip patients: non-routine collection by C&W Lab
 - Spine patients: by bedside nurses in T6
- **Timepoint #5** (6 weeks post-op): non-routine by C&W Lab
- **Timepoint #6** (6 months post-op): non-routine by C&W Lab

Participants may choose not to provide their blood samples and remain a participant for our functional questionnaire and quality of life-related data collection. Analysis of blood will be done in collaboration with the Core Facility for Neurology Biomarker Innovation/[name] Laboratory.

A 3 mL aliquot of the child's blood will be set aside for our study. This blood will be transferred to the appropriate collection tubes (heparin coated) to prevent clotting and will be transported to the BC Children's Hospital BioBank for storage.

A lancing device will be used for finger capillary sampling to collect 50uL of blood from the child. The blood sample will be immediately collected following puncture using capillary tubes and transferred into pre-labeled collection tubes (heparin coated to prevent clotting) and mixed to ensure the sample remains homogeneous. After collection, the sample will be stored at -80 C at the BC Children's Hospital BioBank.

Blood collection of control participants

Control participants will only have their blood drawn at three timpoints. Relative to study participants, blood samples will be collected from controls at:

- **Timepoint #2** (surgery): prior to incision through peripheral venous line by OR staff
- **Timepoint #3** (12-24 hours post-op): through routine venipuncture in T6
- **Timepoint #6** (6 months post-op): non routine bloodwork by C&W lab

At the conclusion of data collection, all blood samples will be transported to the UBC [name] Laboratory (coordinated by the BC Children's Hospital BioBank).

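### The primary consent rate takes no account of whether blood was offered or accepted, so meeting it cannot by itself show that families will join the blood-sampling protocol

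*Protocol*

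**What the plan says.** Under STUDY OBJECTIVES, Primary outcomes, the Protocol defines the first feasibility measure as "Consent rate: The overall average consent rate of children/month". Outcome Measures repeats it: "We will calculate consent rate, which is the overall average consent rate of children/month". The Outcomes list at the end of DATA ANALYSIS gives the pass mark: "Consent rate: An average consent rate of 2-3 children/month". The HYPOTHESIS section expects feasibility to be confirmed "with at least 12 children consented in 1 year and >85% protocol delivery and outcome completion".

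Two provisions let children into that count without blood sampling:

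- STUDY PROCEDURES: "Some participants may be recruited exclusively for functional/quality of life data collection while the team awaits approvals for blood collection and storage", and the stated reason is "to allow for an increased sample size".
- Blood collection of study participants: "Participants may choose not to provide their blood samples and remain a participant for our functional questionnaire and quality of life-related data collection".

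The full schedule for a study participant is three primary visits and six blood timepoints. The baseline finger prick, the 1-2 week draw for hip patients, and the 6-week and 6-month draws are marked as non-routine. The purpose paragraph before SIGNIFICANCE AND JUSTIFICATION explains the pilot by these families' experience of medical trauma, and by the need to settle methods with them before large-scale collection of data that care does not require.

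No section excludes questionnaire-only children or blood decliners from the consent count, splits the rate by period, or reports consent to blood.

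**The concern.** Non-routine blood sampling is the clearest example of the data collection that the pilot is meant to try out. Yet a family that was never asked for blood, a family that declined it and a family that accepted all six collections each add one child to the same numerator, and all months go into the same denominator. The figure cannot separate willingness to complete questionnaires from willingness to join the protocol with blood.

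At stake is how the result is used. If 2-3 per month is reached and reported as feasibility of the study protocol, the larger study could be planned with biomarkers on a recruitment figure that says nothing about them.

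**Working it through.** **Inputs from the Protocol.** Target 12 study participants and 5 controls; about 50 children a year for hip or spine surgery (Sample Size Justification). Expected accrual of at least 12 in 1 year (HYPOTHESIS). Criterion 2-3 per month (Outcomes). The length and accrual of any questionnaire-only period and the proportion declining blood are not given, so steps 2 to 4 use assumed values.

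**1. The Protocol's own figures.** Rate = consents / months.

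- Expected accrual: 12/12 = 1.0 per month. Counting controls: 17/12 = 1.42 per month. Neither reaches 2.
- At the criterion, 12 children would consent in 12/3 = 4 to 12/2 = 6 months. A full year would bring 24 to 36 children, or 24/50 = 48% to 36/50 = 72% of those seen.

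The criterion and the expected accrual do not agree. That is a separate issue, but it limits this one: at 1.0 per month the criterion fails whatever the blood mix.

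**2. Dependence on blood status.** Let d of 12 consents be without blood. Overall rate = 12/months; rate of consents with blood = (12 - d)/months.

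| d | 6 months: overall | 6 months: with blood | 12 months: overall | 12 months: with blood |
|---|---|---|---|---|
| 0 | 2.0 | 2.0 | 1.0 | 1.0 |
| 3 | 2.0 | 1.5 | 1.0 | 0.75 |
| 6 | 2.0 | 1.0 | 1.0 | 0.5 |
| 9 | 2.0 | 0.5 | 1.0 | 0.25 |
| 12 | 2.0 | 0 | 1.0 | 0 |

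The overall columns do not move with d.

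**3. Two periods.** Let f be the share of recruitment time that is questionnaire-only, r1 the rate in that time and r2 the rate once blood is offered. Pooled rate = f·r1 + (1 - f)·r2. The lowest r2 that still gives 2.0 is r2 = (2 - f·r1)/(1 - f).

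| f | r1 = 2.5 | r1 = 3 | r1 = 4 |
|---|---|---|---|
| 0.25 | 1.83 | 1.67 | 1.33 |
| 0.5 | 1.5 | 1.0 | 0 |

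The direction depends on the rates. If r1 = r2, pooling changes nothing. If the questionnaire-only period is slower, for example r1 = 1.5 with f = 0.5, then r2 must be (2 - 0.75)/0.5 = 2.5, and the pooled figure understates recruitment with blood.

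**4. Precision of a split.** Suppose 8 consents in 3 questionnaire-only months and 4 in 3 months with blood. The pooled rate is 12/6 = 2.0; the separate rates are 8/3 = 2.67 and 4/3 = 1.33. Exact Poisson 95% intervals are about 1.2 to 5.3 and 0.4 to 3.4 per month. They overlap widely.

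**The case against.** The strongest reply is that blood is optional throughout, so an overall rate correctly measures enrolment into the study as designed. A family unwilling to give blood can join in either period, and nothing shows that offering an optional component slows enrolment. This stands against one tempting inference: a reader might conclude that an easier early period must raise the pooled rate and hide slower recruitment later. The Protocol does not support that. Questionnaire-only recruitment is only permitted, with no stated length or number, and step 3 shows that the effect could go either way or be nil.

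It can also be said that consent rate is one of four criteria. Protocol delivery, outcome completion and interviews about the methods of data collection might reveal trouble with blood. This stands in part. But the Protocol does not say whether a child without blood is off protocol or incomplete, the interviews reach only enrolled families, and questionnaire-only families have no study draws to describe. None of these measures the uptake of blood sampling among families asked.

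A descriptive breakdown could be left to an analysis plan that is not shown. However, the definition and pass mark of this primary outcome are fixed in the Protocol, and they decide what a pass can mean.

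Finally, biomarkers are a secondary objective, so moving the whole primary criterion to children who consent to blood would be a debatable design choice. That is right, and the fix below does not do so.

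**Conclusion.** The point holds as a limit on what the consent rate can support. As defined, it is unaffected by whether blood was offered or accepted, so a result of 2-3 per month cannot by itself establish that families will join the blood-sampling protocol. This follows from the unrestricted definition. That decliners are counted is inferred from that definition and from their remaining participants; the Protocol does not say so outright.

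The size of any distortion cannot be given. At 12 consents in 6 months, the rate of consents with blood could lie anywhere from 0 to 2.0 per month behind the same overall 2.0. That pace is twice the accrual the Protocol expects. A reader might infer that the pilot is set to pass falsely; at 12 children in 1 year it would instead miss the criterion, with or without blood.

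**What to change.** Keep the overall rate, and state in STUDY OBJECTIVES, Outcome Measures and Outcomes that it measures feasibility of enrolment into the questionnaire component. Define and report in addition:

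- (a) the consent rate over the months when blood collection is open, divided by those months only;
- (b) the number and proportion of children offered blood collection who consent to it.

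Base any feasibility conclusion about the biomarker protocol on (a) and (b).

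The cost is mainly wording. The date on which blood collection opens must be logged, along with whether each child was offered blood and what the family chose at consent. The Protocol does not say that this choice is recorded. The planned log of eligible and approached patients is a natural place for it. Few children and months will lie behind (a) and (b), so they should be given with intervals and read as imprecise, and they may be less favourable than the overall rate. If no questionnaire-only recruitment takes place and no family declines, (a) equals the overall rate, (b) is 100%, and nothing is lost.
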